## **SPECIFIC AIMS**

With the advances in modern neonatal intensive care medicine in the last 20 years, survival of extremely preterm infants weighing less than 1500g (<3 lbs, 5 oz) has risen markedly. However, with this increased survival has come a marked increase in the number of infants with serious neurodevelopmental disabilities: Premature infants with birth weights less than 1500g who survive to go home are at significant risk for serious neurodevelopmental problems: cognitive and motor delays, blindness, deafness, and cerebral palsy. In a recent randomized, placebo-controlled clinical trial, we assessed whether giving mechanically ventilated preterm infants inhaled nitric oxide gas (iNO) for 1 week after birth decreased the incidence of death and chronic lung disease. An unanticipated outcome of that study and a subsequent study of those infants at 2 year of age was that premature infants treated with inhaled nitric oxide (iNO) have improved neurodevelopmental outcomes and physical growth at 2 years corrected age, compared with placebo-treated infants. *INO therapy, therefore, appears to be a new treatment to protect the premature brain during development outside the womb. The overall goal of this application is understand the efficacy of iNO treatment in improving neurodevelopmental outcomes in at-risk premature infants.*

The improvement in neurodevelopmental outcome we reported was primarily due to a decrease in the risk of *cognitive* impairment, measured with the Bayley scales of Infant Development, a standardized tool for assessing neurodevelopmental outcome in this age group. As mentioned above, the initial hypothesis of the study was that iNO therapy would decrease the incidence of death and chronic lung disease. However, we found that the beneficial effect of iNO therapy on neurodevelopment was independent of important clinical factors known to affect neurodevelopmental outcome, including whether infants had chronic lung disease. Furthermore, the magnitude of improvement in neurodevelopmental outcome persisted after statistical adjustment for the presence and absence of intraventricular brain hemorrhage or periventricular leukomalacia (PVL, a softening of the white matter of the brain, due to reduced blood flow). Therefore, iNO therapy appears to be directly neuroprotective in ventilated, preterm infants. The number of children in each group having cerebral palsy, motor delay, blindness, or deafness did not differ between iNO- and placebo-treated infants.

Advances in neonatal intensive care medicine notwithstanding, we have not successfully developed neuroprotective therapies for these at risk preterm infants; iNO therapy, therefore, constitutes the first

intervention to allow the preterm brain to develop normally outside the womb. In our previous study, we treated babies for one week regardless of their level of prematurity. However, we do not know what duration of treatment will result in maximum neuroprotection, and will give the best neurodevelopmental outcome to the most infants. It is likely that maximal benefit of iNO therapy will occur with longer treatment, throughout the preterm period. *Our goal, therefore, is to determine whether iNO therapy given during throughout the preterm period results in further improved neurodevelopmental outcomes, and to understand the biological relationships between iNO treatment and neurodevelopmental outcome.* To achieve this goal, we propose performing a randomized, placebo-controlled, double-blind study of the effect of iNO therapy with gestational age-determined treatment length on neurodevelopmental and growth outcomes of preterm infants. Our Specific Aims are:

**Specific Aim #1. Determine the effectiveness of iNO therapy on improving neurodevelopmental outcome in all O2-dependent premature infants having birth weights < 1500g.** We hypothesize that iNO therapy will improve neurodevelopmental outcome and growth at 18 months postconceptional age compared with placebo treated infants. In a double-blind, placebo-controlled clinical trial, premature infants being cared for in the Intensive Care Nursery at the University of Chicago Medical Center requiring any level of respiratory support will be randomized to receive iNO or placebo gas. Treatment will continue until infants either no longer require supplemental O2 therapy or reach 33 weeks gestational age, whichever comes first. At 18 months postconceptional age, infants will have neurodevelopment assessed and secondary clinical outcomes measured. The relative risks of abnormal neurodevelopmental outcome in the two groups will be compared. The roles played by variables known to independently affect neurodevelopmental outcome, as well as variables known to mediate abnormal neurodevelopmental outcomes will be statistically assessed.

**Specific Aim #2. Assess the mechanisms by which iNO therapy alters neurodevelopmental outcome in preterm infants.** We hypothesize that the amount of nitric oxide delivery to tissues will be positively correlated with neurodevelopmental outcome. Using routinely collected arterial and venous blood from infants in this study, measurements of nitrosylated hemoglobin and nitrite will be made. Arterial-venous differences will be calculated and mean differences compared across treatment groups. Arterial venous

differences will be regressed against neurodevelopmental outcome. Plasma levels of cyclic guanosine monophosphate (cGMP), the intracellular second messenger induced by nitric oxide will also be measured and levels regressed against neurodevelopmental outcome.

## **BACKGROUND**

### **1. Neurodevelopmental outcomes of premature infants**

Improved survival of premature infants has generated intense interest in the quality of life of the survivors. Premature infants have under-developed lungs, brains, digestive tracts, and immune systems. Neurological outcomes for these infants include brain injury (intraventricular hemorrhage, periventricular leukomalacia), blindness, deafness, chronic lung disease, developmental and motor delays and cerebral palsy. The incidence of each of these adverse outcomes increases as infants are born more prematurely. Complicating factors, such as respiratory distress syndrome also has a negative impact on these outcomes. Lower socioeconomic status (SES) also has a marked negative impact, with the risk of abnormal neurodevelopmental outcomes being significantly increased in families with lower SES.

### **2. Prior interventions to improve neurodevelopmental outcome**

The need for effective interventions to improve neurodevelopmental outcomes for these infants has been a topic of concern for a long time. Randomized trials of indomethacin for closure of the ductus arteriosus was found to decrease the most severe form of bleeding in the brain (intraventricular hemorrhage, Grade IV), but a subsequent large randomized clinical trial was able to detect no differences in survival without neurosensory disability at 18 months corrected age. Similarly, a number of trials assessed whether maternal Phenobarbital administration could decrease brain bleeding in very preterm infants < 1000g. While initial reports seemed positive, more modern trials have failed to show differences, either in the rate of severe brain bleeding or in the incidence of adverse neurodevelopmental outcome.

### **3. How does iNO therapy affect neurodevelopmental outcome in preterm infants?**

In our previous single center, double-blind, randomized, placebo controlled study of 207 infants, we

Principal Investigator: [name]

demonstrated that iNO decreases the rate of abnormal neurodevelopmental outcome in infants with birth weights <2000g receiving ventilator therapy for RDS. Our population group was predominantly African-American of low socioeconomic status. The original intent of this study was to assess role of iNO in decreasing death and chronic lung disease (a complication of prematurity and the need for mechanical ventilation). Nitric oxide was given at the dosage rate of 10 parts per million (ppm) for 12-24 hrs, then 5 ppm for up to 7 days, or until extubation. Infants were also randomized to receive either conventional ventilation or high frequency oscillatory ventilation (HFOV), a popular ventilatory approach believed by some to decrease chronic lung disease. We found no differences in the incidence of chronic lung disease and death between the groups receiving one of the two types of ventilator therapy. Our study concluded that nitric oxide in premature infants with respiratory distress syndrome decreased the incidence of chronic lung disease and death, consistent with our primary hypothesis. We also found that infants treated with iNO also had a markedly decreased incidence of the primary neurological complications of prematurity – serious bleeding in the brain (intraventricular hemorrhage) and strokes in the white matter of the brain (periventricular leukomalacia or PVL).

We then followed these infants after discharge for two years. We were able to maintain contact with 82% of those in the original study, a very high follow up rate for this population. In the follow-up study we found that iNO treated infants had decreased abnormal neurodevelopmental outcomes compared with placebo-treated infants. That beneficial effect persisted after statistical adjustment of the outcome for the presence of independent factors known to affect neurodevelopmental outcome: birth weight, gender, exposure to postnatal steroids, as well as factors that mediate abnormal neurodevelopmental outcome – intraventricular hemorrhage/PVL and incidence of chronic lung disease. We were able to conclude, therefore, that iNO has a beneficial, independent effect on neurodevelopmental outcome. We also found that iNO-treated infants grew better. They were only 0.5 standard deviations below the mean of full-term children, compared with more than 1 standard deviation for placebo-treated children.

There have been two other large placebo-controlled, randomized, double blind studies of iNO therapy in premature infants. In a multi-center trial, Kinsella and colleagues at the University of Colorado randomized 793 infants at 34 weeks gestation or less requiring mechanical ventilation to receive 5 ppm of iNO for 3 weeks. They reported no difference in BPD in the overall cohort. However, infants weighing 1000-1250g who received

Principal Investigator: [name]

iNO had a significantly reduced incidence of chronic lung disease compared with the placebo-treated group. Most excitingly, for the entire cohort, the incidence of the combined end point of IVH, PVL and ventriculomegaly (all signs of brain injury) was significantly reduced in iNO treated group over the placebo-treated group. This study provides support for our single center study that iNO therapy reduces overall risk of brain injury. It is also of importance to note that iNO was given for periods up to three times as long as our study, and without any adverse outcome.

Ballard et al from the Children's Hospital of Philadelphia reported on their randomized double blind placebo-controlled, multi-center study of 582 infants weighing < 1250g who were on mechanical ventilation or continuous positive airway pressure (CPAP). In that study iNO was started later, at between 7 and 21 days of life. In contrast to our study, iNO was begun at a higher dose (20 ppm), then weaned first at 96 hrs of treatment and then weekly. Patients were treated for a minimum of 24 days. The primary outcome was survival without chronic lung disease. iNO was shown to decrease the incidence of survival without BPD. However, neurodevelopmental outcomes were not evaluated. However, this study confirms our initial study's findings that iNO decreases BPD. Taken together these two studies provide confirming evidence that, in preterm infants, iNO therapy decreases BPD and brain injury.

#### **4. What are the mechanisms by which iNO therapy alters neurodevelopmental outcome in preterm infants?**

In studies of brain injury in animals, nitric oxide (NO) has been associated with neuroprotection, mostly likely through actions on the blood vessels of the brain. After inhalation, iNO crosses the alveoli (air sacs) of the lung and enters the circulation, where it is bound to hemoglobin. It had been believed that NO bound to hemoglobin was inactivated. How, then could inhaled NO be delivered to target tissues, such as the brain? New data indicate that hemoglobin may act as a delivery system for NO to target tissues. Neuroprotection may be due to actions of NO on blood vessels in the brain, with its ability to increase blood flow to injured areas of the brain.

In the laboratory component of this study, we propose to measure NO metabolites in the blood of our study babies treated with iNO or placebo. Recent data now suggest that NO, both administered as well as naturally

produced, is transported in blood to target tissues, where it can increase local blood flow. This has been documented in humans, where inhalation of NO was found to increase blood flow in the arm of exercising volunteers. Furthermore, NO has been shown to be carried on the hemoglobin molecule in red blood cells – the hemoglobin becomes nitrosylated, carrying an NO molecule. Thus, iNO markedly elevates levels of total nitrosylated hemoglobin in human volunteers. Most importantly, there is a marked difference in the amount of nitrosylated hemoglobin between the arterial circulation carried to the tissues, and the venous circulation carried away from the tissues. This difference indicates that inhaled NO delivered in the arterial blood is being removed from hemoglobin in the tissues, consistent with its effect in organ capillary beds. In addition to nitrosylating hemoglobin, plasma nitrite also appears to be a source of bio-available NO. Nitrite, generated from the reaction of NO with oxygen, can be converted back to NO by means of naturally occurring enzymes in the body. In fact, similar to levels of nitrosylated hemoglobin, large differences in arterial and venous nitrite levels have been documented in humans, and has been shown to be bioactive.

In the laboratory component of this study, we propose to measure NO metabolites in blood in children treated with iNO or placebo, and calculate the NO delivery to tissues using arterial and venous measurements. We will describe the time course of these metabolites during the course of iNO therapy, and correlate the level of NO metabolites with neurodevelopmental outcome.

## **SIGNIFICANCE**

Despite much research into potential neuroprotective treatments for premature infants, the risk of abnormal neurodevelopmental outcome persists. Concurrently, the number of surviving preterm infants is rising because of advances in neonatal intensive care medicine. Inhaled nitric oxide is the only treatment shown to improve neurodevelopmental outcome in preterm infants. The results from the proposed study will establish whether iNO is effective in improving neurodevelopmental outcome for the vast majority of premature infants, i.e. those infants needing some respiratory support. If our hypothesis is upheld, iNO it has the potential to markedly impact the quality of life for these babies and their families.

## **RESEARCH PLAN**

**Overall Experimental Plan:** The study is a single-site, randomized, double-blind, placebo-controlled trial of inhaled nitric oxide therapy in all preterm infants with any respiratory disease who weigh <1500g at birth. The trial is designed to treat these infants with nitric oxide from birth to 33 weeks gestation – a critical period of brain development in preterm infants. Our primary objective is to compare neurodevelopmental outcomes between our iNO and placebo-treated patients. We also wish to study the mechanisms underlying the protective effect of iNO, by assessing the relationship between nitric oxide delivery to tissues and neurodevelopmental outcome.

The major differences between this study and our previous study are:

- 1) Inclusion of all preterm infants requiring at least supplemental oxygen therapy. Approximately half of all infants weighing <1500 at birth do not require mechanical ventilation with a breathing machine, which was one criterion for inclusion in our previous study. However, these infants are still at risks for abnormal neurodevelopmental outcomes. By including all infants requiring at least supplemental oxygen by nasal cannula, we hope to obtain information regarding the potential beneficial effects of iNO applicable to the majority of at-risk preterm infants.
- 2) Gestational age-dependent duration of iNO therapy. In our previous study, infants were treated with iNO or placebo for 7 days (if still on mechanical ventilation). Consequently, infants received iNO therapy during different periods of brain development: for example, infants of 24 weeks gestation (16 weeks early) received iNO during a period during brain cells were being rapidly produced, while infants of 30 week's gestation received iNO after brain cells had been made and were now forming connections. In this study, our goal is to provide iNO during the entire time the premature brain is developing outside the womb. Therefore, infants will be treated from birth until 33 weeks gestation, so that less mature infants will be treated for a longer time.
- 3) Specific design of the study to assess neurodevelopmental outcome. Our previous study had been designed to assess the effect of iNO treatment on the incidence of chronic lung disease and death; we assessed these infants' neurodevelopmental outcomes because of our unanticipated finding of decreased brain bleeding and softening. This study has as its primary outcome the incidence of abnormal neurodevelopmental outcome.
- 4) Laboratory-based Specific Aim to assess the mechanisms of the iNO-induced neuroprotection.

**Specific Aim #1. Assess the role of iNO therapy on neurodevelopmental outcome in all oxygen-dependent premature infants having birth weights < 1500g.**

(i) *Rationale.* We have previously found that brief (1 week) treatment of ventilated preterm infants reduces abnormal neurodevelopmental outcome. Because brain development continues throughout gestation, we hypothesize that iNO therapy will be protective to the preterm brain if given from birth until the risk for abnormal neurodevelopmental outcome is similar to that of term infants.

(ii) *Study design.* We have designed a randomized, placebo controlled, double blind study of iNO therapy during Intensive Care Nursery stay, followed by blinded neurodevelopmental assessment at 18 months corrected age, a commonly used developmental endpoint.

(iii) *Patients.* All premature infants cared for in the Intensive Care Nursery at the University of Chicago Medical Center, who are less than 72 hours old, weighing less than 1500 grams at birth, and requiring any respiratory support, will be eligible for the study. Enrolled infants are anticipated to have the same demographics as we have previously reported: 52% male, 70% African-American, 45% single parent household. Potential subjects will be identified and informed consent sought, if possible, prior to birth, otherwise, within the first 3 days after birth.

(iv) *Exclusion criteria.* Those infants with severe congenital anomalies, including major congenital heart disease, or major kidney, lung or brain malformations will be excluded, as will be those infants with a genetic syndrome. Infants judged by the physician to not be viable will be excluded from the study, as will extremely sick infants requiring very high ventilatory pressures (Oxygen Index  $\geq 20$ ). This latter group is excluded because of a previous study by Van Meurs which showed that infants in this category are made worse by inhaled nitric oxide.

(v) *Patient randomization.* Randomization will be performed as we have previously published. To keep birth-weight distribution comparable in the two groups, we will use five 250-gram-birth weight strata for randomization. To ensure equal enrollment in the two groups, infants will be randomly assigned within each stratum, according to a permuted block design to receive inhaled nitric oxide (INOmax®, INO Therapeutics) or

oxygen placebo. This strategy provides a balanced group assignment with every 4 enrollments.

(vi) *Patient enrollment at study entry procedures.* We will enroll patients and enter them into the study as we have previously published. Briefly, potential subjects will be identified, prenatally if possible, and the parents approached for informed consent. With consent obtained, and the infant born, admitted, and verified to meet inclusion criteria, a sealed envelope containing the randomized treatment assignment, appropriate identifying labels, etc., will be pulled and opened by the respiratory therapist. Documentation of the treatment assignment and patient data will be recorded by the respiratory therapist in the study book (kept in the respiratory therapy room), and an INOvent® brought to the bedside. The INOvent will be set to deliver either iNO or oxygen according to the treatment randomization and then covered to conceal the treatment group from the caregivers and investigators.

(vii) *Treatment.* iNO or placebo (oxygen) will be given 5 ppm while ventilated or on continuous positive airway pressure (CPAP) and 10 ppm while on nasal cannula oxygen. In infants receiving iNO by nasal cannula, iNO concentrations are set to 10 ppm, because previous studies have shown that delivery 10 ppm by nasal cannula results in nasopharyngeal concentrations of about 5 ppm^9. These dosages will continue until the infant no longer needs supplemental oxygen or reaches 33 weeks post conceptional age. All infants will have iNO delivery devices (INOvents) at the bedside to deliver either iNO or O2, and will be shrouded to hide from caregivers the nature of the gas being delivered. Only respiratory therapy and data safety monitor to know of gas assignments.

(viii) *Data Collection.* Clinical data (fluids, medications, diagnoses, ventilator settings) will be collected daily by our research professional.

(ix) *Sample size.* In our previous study of infants with RDS, iNO treatment cut the risk of abnormal neurodevelopmental outcome by half. The baseline incidence of abnormal neurodevelopmental outcome is 40% in this age group by published NICHD data. Therefore to see a decrease of abnormal neurodevelopmental outcome to 20% (half of baseline incidence) with 80% power, 82 babies are needed in each arm of the study, for a total of 164 babies. We have previously published an overall mortality rate for intubated infants < 2000g in our nursery of 23%. Because we are including non-intubated infants, we

estimate a mortality rate of about 18%. Therefore, to ensure sufficient infants surviving to follow up, we anticipate needing to enroll approximately 215 babies over 18 months. With a historic 80% follow-up rate, we will need a total of 268 infants. Every year we admit approximately 175-200 infants with birth weights < 1500g. We therefore anticipate enrollment taking as long as 18 months. Our non-consent rate historically is < 10%.

(x) *Standards of neonatal intensive care.* Because we have shown no effect of ventilatory strategy on neurodevelopmental outcome, there will be no external control of ventilatory modality. Because this is a single-site study, variability in practice exists only between our eight member group of neonatologists, with constant care provided by nurse practitioners, residents, and nursing staff.

(xi) *Safety monitoring.* As per our clinical routine, methemoglobin is regularly monitored with arterial blood gases. Although we and others have shown that iNO therapy is safely used in preterm infants, interim safety analyses will be performed when 50% of patients enrolled. Deaths will be compared, as will the incidence of severe intraventricular hemorrhage, and tests of significance made with Chi-square. The study will be stopped if the incidence of either index in the iNO groups is significantly higher than in placebo groups.

(xii) *Primary Outcome.* As we have published, we will measure abnormal neurodevelopmental outcome at 18 months corrected age. Three disability levels will be assessed: disability (cerebral palsy, blind in both eyes, or deaf in both ears); delay (score on Mental or Psychomotor Developmental Index of the Bayley Scales of Infant Development < 70 without a disability) or normal (without disability or delay).

(xiii) *Secondary Outcomes.* Other neurodevelopmental outcomes to be measured include the incidences of disability or delay; mean cognitive (MDI) and psychomotor (PDI) function scores will be obtained and infant growth charted. Important clinical diagnoses known to affect the risk of adverse neurodevelopmental outcomes will be tracked: respiratory distress syndrome, bronchopulmonary dysplasia, necrotizing enterocolitis, intraventricular hemorrhage (with grade), periventricular leukomalacia, retinopathy of prematurity, and failed hearing screen. Finally, detailed clinical data will be tracked on a daily basis, including fluids, ventilatory status, blood gases, feedings, etc.

(xiv) *Measures to ensure long-term neurodevelopmental follow-up.* The very high follow-up rates we have previously published require intensive efforts of a number of teams following a patient's discharge, including social services and the research staff. All preterm infants will be followed in our high risk follow-up clinic. This clinic is unusual, in that it provides routine, well-child care to its babies, as well as subspecialty care and neurodevelopmental care. Providing routine care provides an important incentive to parents to come to clinic, since they only have one appointment to make. In addition, we provide regular reminders of the role of the University of Chicago Medical Center in the lives of our families: patients receive holiday and birthday cards, and personalized invitations to our regular patient reunions. Finally, families who come for follow-up visits are given gifts and their travel expenses are reimbursed. Families are rewarded at a 9 month follow-up visit and at the 18 month follow-up visit. With this approach, our drop-out rate is less than 15% -- very low for this population by published reports.

(xv) *Assessment of neurodevelopmental outcome.* As we have previously published, at 18 months post conceptional age, developmental screening with Bayley exams will be performed in our High Risk Follow-up Clinic by [name], who will also perform neurological examinations to identify those infants with cerebral palsy. Other assessments will include measurements of physical growth and review of routine visual and hearing examinations to determine blindness or deafness. Questionnaires assessing socioeconomic status and self report of racial ethnicity will be administered. All examiners will be unaware of treatment regimen assignment. In our previous studies, our follow-up rate of >80% is very high by published standards, especially for an inner city community such as we serve. We anticipate that rate will continue for the current study.

(xvi) *Data analysis.* As we have previously published, data will be analyzed as "Intent to Treat." . Clinical and demographic variables between groups will be compared with Fisher's exact test for categorical variables and Wilcoxon rank-sum tests for continuous variables. Primary outcomes will be analyzed with generalized linear models to obtain relative risks of primary outcome in the two groups. Effects of potential confounders will be adjusted for in the model: birth weight, sex, socioeconomic status, as well as for potential the intermediate variables: prolonged exposure to postnatal steroids, presence of chronic lung disease, severe IVH, or periventricular leukomalacia (PVL). Further analyses of Bayley scores, both cognitive (MDI) and psychomotor (PDI) will be performed.

(xvii) *Anticipated results and critique.* We anticipate that infants treated with iNO will demonstrate significantly decreased incidences of abnormal neurodevelopmental outcomes and will also demonstrate significantly increased cognitive abilities, as demonstrated by MDI scores. We further anticipate that these effects will persist after statistical adjustment for factors independently predisposing to abnormal neurodevelopmental outcome, such as male gender and gestational age, as well as adjustment for factors potentially mediating adverse neurodevelopmental outcome, such as chronic lung disease, intraventricular hemorrhage, or PVL.

In our previous study, we found that some infants tolerated our standard weaning protocol from iNO poorly, requiring much slower weaning and therefore a longer time on very low concentration (1-2 ppm) of NO. One mechanism underlying this minor complication is decreases in native NO production by blood vessels of the lung during prolonged periods of iNO delivery. Therefore, it is conceivable that extremely preterm infants, who will, by design, receive iNO for up 8 or 9 weeks, exhibit intolerance to weaning off iNO. Accordingly, we will wean patients by 1 ppm every 12-24 hrs, the protocol which served us well in the previous study in this setting.

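### Respiratory support at entry is never used in the analysis, so a difference in effect between ventilated and non-ventilated infants would go unexamined, although including the latter is the trial's first-listed extension

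*Combined protocol and SAP*

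**What the plan says.** **Objective.** The Research Plan states: "Our primary objective is to compare neurodevelopmental outcomes between our iNO and placebo-treated patients". Specific Aim #1 covers all oxygen-dependent infants under 1500 g.

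**Extension.** Item 1 of the listed differences from the previous study widens entry beyond mechanical ventilation. The reason given is that "Approximately half of all infants weighing <1500 at birth do not require mechanical ventilation with a breathing machine", and the stated hope is that "we hope to obtain information regarding the potential beneficial effects of iNO applicable to the majority of at-risk preterm infants". The Significance section says that the results will settle whether iNO is effective "for the vast majority of premature infants, i.e. those infants needing some respiratory support".

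**Source of the effect size.** The Aim #1 rationale (i) describes the previous study's result as "brief (1 week) treatment of ventilated preterm infants reduces abnormal neurodevelopmental outcome". Sample size (ix) starts from the statement that "iNO treatment cut the risk of abnormal neurodevelopmental outcome by half" and applies that halving to one overall control rate of 40%.

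**Design and analysis.** Randomisation (v) is stratified by birth weight only. Data analysis (xvi) estimates a relative risk between the two arms and says "Effects of potential confounders will be adjusted for in the model: birth weight, sex, socioeconomic status", followed by a list of intermediate variables. Support at entry does not appear as a stratum, a covariate, an interaction term or a group in which the effect is estimated.

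**The concern.** The part of the enrolled population that is new to this trial is the part for which the centre has no neurodevelopmental evidence. The Background describes one other trial that admitted infants on CPAP, but says that neurodevelopment was not evaluated there. Whether the effect carries over from ventilated infants is therefore an open question that this trial is well placed to inform.

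Under the plan as written, one pooled relative risk would be reported. An effect present in both groups and an effect confined to ventilated infants could give similar pooled figures. If the effect is confined, two errors are possible. A diluted, non-significant result may hide a real effect in ventilated infants. Or a significant result carried by ventilated infants may be applied to infants who gained nothing. A split made after the data are seen would be open to the charge that it was chosen for its result.

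**Working it through.** **Inputs from the protocol, (ix):** control rate 40%, treated rate 20%, 80% power, 82 per arm (164 evaluable), 18% mortality, 80% follow-up, 268 enrolled.

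**Assumptions not in the documents:** two-sided 5%; a non-ventilated share of enrolled infants between 30% and 50%; control rates by support. The protocol's half refers to all infants under 1500 g. Infants needing no support are ineligible, so the enrolled share may be lower.

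**Step 1. Reproduce the plan's figure.**

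n = [1.96·√(2·p̄·(1−p̄)) + 0.8416·√(p1(1−p1) + p2(1−p2))]² / (p1−p2)²

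With p1 = 0.40, p2 = 0.20, p̄ = 0.30: [1.96·0.648 + 0.8416·0.632]² / 0.04 = 81.2, rounded up to 82. This matches. Power at 82 per arm is 80.4%.

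**Step 2. Pooled power if only ventilated infants benefit (relative risk 0.5; 1.0 in the others).**

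With non-ventilated share s and control rates pv (ventilated) and pn (non-ventilated):

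- pooled control = (1−s)·pv + s·pn
- pooled treated = (1−s)·0.5·pv + s·pn
- power = Φ{[d·√n − 1.96·√(2·p̄·(1−p̄))] / √(p1(1−p1) + p2(1−p2))}, where d is the difference in rates and n = 82

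Example, s = 0.5 and 40% in both: treated = 0.5·0.20 + 0.5·0.40 = 30%. Power = Φ[(0.10·9.055 − 1.96·0.6745)/0.6708] = Φ(−0.62) = 27%.

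| Share non-ventilated | Control rate, ventilated / non-ventilated | Pooled control vs treated | Power |
|---|---|---|---|
| 50% | 40% / 40% | 40.0% vs 30.0% | 27% |
| 50% | 50% / 30% | 40.0% vs 27.5% | 39% |
| 50% | 55% / 25% | 40.0% vs 26.25% | 46% |
| 40% | 40% / 40% | 40.0% vs 28.0% | 37% |
| 40% | 55% / 25% | 43.0% vs 26.5% | 60% |
| 30% | 40% / 40% | 40.0% vs 26.0% | 48% |
| 30% | 50% / 30% | 44.0% vs 26.5% | 65% |
| 30% | 55% / 25% | 46.0% vs 26.75% | 73% |

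In the rows with a smaller share and unequal control rates, the pooled control rate exceeds the plan's 40%, which accounts for part of the higher power.

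**Step 3. What a split by entry support would deliver (half share, 41 per arm, 40% control).**

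- SE of log RR at 40% vs 20% = √[0.6/(41·0.4) + 0.8/(41·0.2)] = √0.134 = 0.366. The 95% CI for an RR of 0.5 is 0.5·exp(±1.96·0.366), or 0.24 to 1.03.
- Power for 40% vs 20% with 41 per arm is 51%. At a 30% share (0.30·82 = 24.6 per arm) it is 33%.
- Interaction, RR 0.5 versus 1.0: the SE in the no-effect half is √[2·0.6/(41·0.4)] = √0.073. The combined SE is √(0.134 + 0.073) = 0.455. Power = Φ(0.693/0.455 − 1.96) = 33%.

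**Step 4. What a confirmatory answer would need.** At a half share, 82 per arm in non-ventilated infants means 328 evaluable in all. Enrolment would be 328/(0.82·0.80) = 500, against the planned 268.

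**The case against.** The strongest reply is that the plan answers its own question. Its objective is the comparison of arms in the whole supported population, and a pooled intention-to-treat analysis is the right primary analysis for that. A reader might infer that benefit in non-ventilated infants is itself a stated objective left unanswered. The documents do not support this: including them is a design difference, worded as a hope, and the Significance section speaks of establishing whether iNO works in the supported population. This part of the reply stands.

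A reader might also infer that the different cannula setting makes non-ventilated infants a separately dosed group. Treatment (vii) explains that setting as a way to reach a similar nasopharyngeal concentration, and infants on CPAP share the ventilated setting. Systematically shorter courses in non-ventilated infants are likewise an inference, since duration also depends on gestational age. Neither argument is relied on here.

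Nor do the documents show that a pooled positive result would probably come from ventilated infants alone. To come close to the planned result at a half share takes a stronger effect than the protocol's halving. With 55%/25% control rates and a relative risk of 0.3 in ventilated infants, the pooled rates are 40% vs 20.75%, with power about 77%. With the protocol's 0.5 and the same control rates, power is 46%.

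Finally, the split is weak: 51% power in the non-ventilated half and 33% for the interaction. It will rarely separate the two explanations. That is a reason to label it exploratory and not to let a claim rest on it alone. It is not a reason to omit it, because an interval fixed in advance is more informative than none.

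**Conclusion.** The concern holds as an omission from the analysis plan, not as a defect in the primary comparison. The trial extends treatment to infants outside its own prior evidence, applies the effect seen in ventilated infants to all, and plans no look at whether the effect differs by support at entry.

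If risk is halved only in ventilated infants, pooled power is about 27% to 46% at a half share and 48% to 73% at a 30% share, against the planned 80%. At a half share a diluted, non-significant result is the likelier outcome. At a smaller share a pooled positive driven by ventilated infants is plausible. Either would pass unnoticed, but misreading is a risk and not a certainty. The range rests on the assumed significance level, enrolled share and subgroup control rates, none of which the protocol gives. That the variable is absent from (v) and (xvi) rests on no assumption.

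**What to change.** In Specific Aim #1 (xvi):

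1. Add respiratory support at randomisation to the baseline covariates of the primary model.
2. Pre-specify one secondary, exploratory analysis: the treatment relative risk with 95% CI by support at randomisation (ventilated versus CPAP or nasal cannula), with the treatment-by-support interaction. Label it low-powered and quote the expected precision from Step 3.
3. Use status at randomisation, not later status, because later support can itself be affected by treatment.
4. State that any conclusion about non-ventilated infants will report that group's estimate and interval beside the pooled result, and that a non-significant subgroup result will not be read as no effect.

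The primary comparison and the sample size stay as they are. The cost is a few lines of text and wide subgroup intervals. Ventilator settings are already collected daily under (viii), so the only practical step is to make sure that the status at randomisation is identifiable.
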